Pulmonx Corporation

Clinical Investigational Plan #630-0012_H

Statistical Analysis Plan – Revised 26 October 2017 (supersedes Appendix 19 from CIP #630-0012_H)

Change History:

SAP Section	Change	Rationale
Study Design	Update the enrolled study participants to 190.	To reflect the number of study participants enrolled in the study.
Secondary Effectiveness Endpoints	Analyses of secondary endpoints were updated to limit the number of statistical comparisons. Now limited to Absolute Change in FEV1, 6MWD, and SGRQ score. The use of Hochberg method was specified to address multiplicity.	To control the family-wise Type I error for the secondary endpoints, analyses of secondary endpoints were limited.
Safety Endpoint	Deleted "of the EBV treatment arm".	To reflect that adverse events will be compared between treatment arms during the short-term and long-term periods.
Additional Measures	Additional measures were updated, specifically, Treatment Lobe Volume Reduction (TLVR) for the treatment arm only was moved from Secondary to Additional.	Moved to "Additional Measures" since this parameter indicates the mechanism of action and unable to compare to a Control group as no TLVR is expected without an intervention.
Statistical Methods – I	Confidence intervals were removed from adverse event reporting. In place of presenting confidence intervals, adverse event rates for those events occurring in at least 3% of subjects in either group will be compared using a Fisher's Exact test.	Making adverse event reporting consistent with typical way of presenting and analyzing adverse events.
Statistical Methods II (C)	Pseudo-sites clarified to be created from sites within the same country.	Clarification.
Statistical Methods III	Definitions of populations clarified.	Clarification.
Statistical Methods IV	Update to "three" secondary effectiveness variables in the text and in Table 3.	To reflect the modified secondary effectiveness endpoints.
Statistical Methods IV (B)	Update to analyses of secondary endpoints, including use of Hochberg method.	To control the family-wise Type I error for the secondary endpoints,

		analyses of secondary endpoints were limited.
Statistical Methods IV (C)	Update to analyses of additional effectiveness endpoints.	As a result of modifying the secondary effectiveness endpoints, additional measures were also updated.
Statistical Methods V	Clarify that covariate analyses are to be performed on primary and secondary endpoints only. Removed variables that will not have data available for control subjects.	Clarification.
	Deleted "Follow-up" column as no "Follow-up" variables will be used in covariate analysis.	
Safety Analyses VII	Updated to include Control arm in summary of adverse events and specify Fisher's Exact tests of events occurring in at least 3% of either treatment arm.	In place of presenting confidence intervals, adverse event rates for those events occurring in at least 3% of subjects will be compared using a Fisher's Exact test.
Statistical Methods IX	Included imputation strategy for subject deaths and clarified secondary endpoints would utilize same imputation method as primary endpoint.	Subject death prior to endpoint visit should be considered a failure. Secondary endpoints should account for missing data.
Statistical Methods X	Clarification to statistical tests.	Clarification.
Other	Tables and text formatted.	Ease of reading.

Analysis Summary

Study Title: Lung Function Improvement after Bronchoscopic Lung Volume Reduction with Pulmonx Endobronchial Valves used in Treatment of Emphysema (Clinical Protocol 630-0012).

Patient Population: Male and female patients with severe heterogeneous emphysema meeting the study eligibility criteria.

Study Design: This will be a multi-center, prospective, randomized, controlled study with EBV treatment statistically evaluated using Intent-to-Treat (ITT) analyses. A maximum of 183 ITT study participants, who meet study entry criteria, consisting of screening eligibility criteria, baseline eligibility criteria, and procedure eligibility criteria, were planned to be enrolled. A total of 190 study participants were enrolled. Safety and effectiveness of bronchoscopic lung volume reduction (BLVR) using the Pulmonx EBV will be evaluated at 1 year. An interim analysis designed to evaluate effectiveness for continuing crossover of control participants at 1 year to EBV treatment will be performed when 74 study participants have completed the 1-year follow-up. For study participants who have been treated with EBV, a secondary valve intervention such as valve removal, replacement, or adjustment may be considered during the study follow-up. Long-term data will be collected annually for EBV-treated study participants through 5 years. Per the regulatory plan agreed to with FDA, 1-year of follow-up is required pre-approval and the remaining 4 years of follow-up will be conducted post-approval.

Primary Effectiveness Endpoint

The percentage of study participants in the Endobronchial Valve (EBV) treatment arm who meet the threshold of \geq 15% improved forced expiratory volume in one second (FEV₁) as compared to the control arm at 1 year. Improved FEV₁ will be calculated by determining the percentage change for FEV₁ from baseline to 1-year post-procedure for individual study participants.

Secondary Effectiveness Endpoints

- 1) FEV₁: Difference between study arms in 'absolute change from baseline' for FEV1 at 1 year.
- 2) 6-Minute Walk Distance (6MWD): Difference between study arms in 'absolute change from baseline' for 6MWD at 1 year.
- 3) St. George's Respiratory Questionnaire: Difference between study arms in 'absolute change from baseline' for SGRQ score at 1 year.

Safety Endpoint

Evaluation of the short- and long-term adverse events profile during the treatment period, defined as the day of the study procedure until 45 days after the study procedure (short), and in the post-treatment period, defined as 46 days after the study procedure until the 1-year followup visit (long).

Additional Measures

- Treatment Lobe Volume Reduction (TLVR) for the treatment arm only
- Spirometry, including FEV₁, forced vital capacity (FVC) and the ratio of FEV₁/FVC
- Body plethysmography, including residual volume (RV), inspiratory capacity (IC), functional residual capacity (FRC), TLC, and the ratios of RV/TLC and IC/TLC
- SGRQ Total and domain (i.e. 'symptoms', 'activity' and 'impacts on daily life') scores
- Modified Medical Research Council (mMRC) Dyspnea Scale Score
- BODE Index
- Transitional Dyspnea Index (TDI) from Baseline Dyspnea Index (BDI)
- COPD Assessment Test (CAT)
- SF-36 Health Survey score
- EQ-5D Health Survey score
- Health Care Utilization Questionnaire
- 6MWD test
- Borg scale dyspnea scores before and after 6MWD test
- Change in use of 'maintenance' medications, including bronchodilators, corticosteroids, antibiotics, and anti-inflammatories
- Pulmonary rehabilitation compliance diary responses
- EXACT-PRO diary responses
- Health status change responses
- Carbon Monoxide Diffusing Capacity (DL_{CO})
- Lung radiographic features

Interim Analysis

An interim data analysis designed to evaluate effectiveness for continuing crossover of control arm study participants at 1-year to EBV treatment will be performed when 74 (50% of the total 147) study participants have completed the 1-year follow-up. The interim analysis will be reviewed by the DSMB and FDA. If crossover of control arm study participants is found to be justified by the interim analysis, then crossover of control arm study participants may be continued. If the DSMB recommends not continuing crossing control arm participants to EBV treatment, then those control arm patients who have not yet crossed over will exit from the study per protocol after the 1-year visit.

Long-Term Follow-up

Data will be collected annually through 5 years. Per the regulatory plan agreed to with FDA, 1 year of follow-up is required pre-approval and the remaining 4 years will be conducted post-approval. The 2-, 3-, 4-, and 5-year data will consist of FEV₁ and adverse events.

Definition of Study Success: The study will be a success if the difference between the EBV Treatment arm and Control arm for the percentage of study participants meeting the threshold of \geq 15% improved in FEV₁ differs significantly (two-sided test at p<0.05) in favor of the treatment group at 1 year. This evaluation will be conducted at 1-year post-randomization.

Number of Study Participants: 190

Statistical Methods

I. Descriptive Statistics

Means, standard deviations, medians, and confidence intervals will be reported for all continuous variables. Dichotomous variables will be reported as percentages and the numerator and denominator will be reported and defined.

II. Analyses of the Patient Populations

These analyses are intended to determine the similarity of two treatment groups and similarity of patients from different study sites with respect to important demographic or other variables, either known or suspected to have an influence on the outcome variables. The absence of similarity for any variable will identify that variable as a potential covariate in subsequent analyses.

- A. Comparability of Treatment Groups To assess the success of the randomization process, the demographic and prognostic variables measured at study entry will be compared between the Treatment and Control arms. Continuous variables will be compared with the two-sample t-test or the Wilcoxon two-sample rank test, and categorical variables will be compared with the Fisher's exact test or a Chi-square test. Comparability analyses will be done with two-sided tests with significance level of 0.05.
- B. Study Site Comparability –The appropriateness of pooling the data across study sites will be determined on a clinical basis, i.e., to ascertain if the sites used a common protocol, the sponsor adequately monitored the study to assure protocol compliance, and the data gathering and validation mechanisms were the same across all study sites (Meinert, 1986).

An analysis will be done to determine if the magnitude of the clinical effect of the primary outcome is maintained if sites and/or site by treatment interactions are included in an analysis of covariance model. We expect the majority of sites will show the treatment to be beneficial but statistically one would not expect all sites to show the treatment to be beneficial. For those sites with contrary results, an analysis will be attempted to determine what factors at those sites led to the result (See expert statistical testimony from Dispute Resolution Panel transcript September 6, 2001).

C. In study sites with small numbers of patients, it will not be possible to evaluate site or site by treatment interaction. The reason is that what may appear to be a site by treatment interaction may be a small numbers phenomenon. For example, if there were only three patients from a given study site with one in the control group and two in the treated group, one success in each arm will appear to be a site by treatment interaction (100% success in the controls but 50% success in the treated arm). Hence, study sites, within the same country, with fewer than three patients in either treatment arm will be combined into one or more pseudo-sites to allow the comparison to be done. The size of any pseudo-site created in this way will not exceed the size of the study site with the largest enrollment.

III. Analyses Populations

- A. Geographic Cohort: This study will be conducted at clinical sites inside and outside the U.S.
- B. Endpoint Analyses: Primary and secondary study endpoints will be analyzed utilizing an intent-to-treat (ITT) population defined as all randomized patients analyzed by the groups to which they were randomly assigned (EBV treatment or control).
- C. Secondary Analyses: Secondary analyses will also be performed on the study primary and secondary endpoints on a Completed Cases (CC) basis and Per-Protocol (PP) basis.
 - i. The CC population is defined as all randomized and eligible patients who received study-directed treatment and attended the 1-Year follow-up visit.
 - ii. The PP population is defined as all randomized patients who meet study eligibility criteria, who were treated as randomly assigned, and had follow-up within window for the primary endpoint (i.e., 1-Year FEV₁). Any visits where protocol violations occurred will be reviewed for possible exclusion from impacted analyses.
- D. Safety Analysis Population: Both the ITT analysis population and 'As Treated' (AT) analysis population will be used to assess the safety data. For the AT analysis, study participants will be analyzed based on the treatment they actually received.
- E. Secondary Valve Procedures: If applicable, statistical analyses will also be conducted after sorting patients by the actual treatment received, specifically valve removal, valve replacement, and valve adjustment.
- IV. Effectiveness Analyses

There is one primary effectiveness variable, three secondary effectiveness variables, and several additional effectiveness variables.

A. Analysis of the Primary Effectiveness Endpoint

Both an interim and an end of study analysis for the primary effectiveness endpoint are planned. The primary effectiveness endpoint is the difference between the EBV treatment arm and control arm in percentage of study participants who reach a threshold of \geq 15% improved FEV₁, collected post-bronchodilator, at 1 year (see Table 1). The FEV₁ value will be calculated by determining the percentage change for FEV₁ from baseline to 1-year post-procedure using: ((FEV₁ at 1-year follow-up subtracted from FEV₁ at baseline) / (FEV₁ at baseline)) for individual study participants. The two arms will be compared using the standard normal Z-statistic.

Table 1. Primary Effectiveness Endpoint

Variable	Unit	Values Statistically Evaluated
Forced Expiratory Volume (FEV ₁)	>15% improved	percentage of participants

An interim data analysis designed to evaluate effectiveness for continuing crossover of control arm study participants at the 1-year follow-up to EBV treatment will be performed when 74 (50% of the total 147) study participants have completed the 1-year follow-up. The interim analysis will be reviewed by the DSMB.

To account for the interim analysis, the power spending function, defined as:

$$\alpha(t) = \alpha t^{\phi}$$

will be used to preserve an overall type I error rate of 0.05 for the study. Using the nTerim program (Statistical Solutions) to calculate the power spending function with: $\alpha = .05, \phi = 2.3 \text{ and } t = .5, \alpha(t) = .01,$

the value of the Z-statistic must exceed 2.571 (nominal alpha <0.01) for the null hypothesis to be rejected at this interim look (see Table 2).

 Table 2. Power Spending Function for Interim Analysis

Looks	1	2
Time	0.5	1
Lower Bound	-2.57057	-2.00360
Upper Bound	2.57057	2.00360
Nominal Alpha	0.01015	0.04511
Incremental Alpha	0.01015	0.03985
Cumulative Alpha	0.01015	0.0500
Exit Probability	38.75	50.52
Cumulative Exit Probability	38.75	89.28

If Z \geq 2.571 then continuing crossover of control arm study participants will be strongly justified since the p-value will be \leq 0.01. This observation may provide evidence to stop the trial early.

The study hypothesis will be tested again at the end of the study. The Z-statistic will be calculated again, and by taking into account the interim analysis, will have a final critical boundary value of 2.004, per the nTerim program. If the trial is not stopped as a result of the interim analysis, then the final Z-statistic must be greater than or equal to 2.004 in order to reject the null hypothesis at the final analysis (at the overall 2-sided 5% significance level). Test statistic is "Z" as defined as:

$$Z = \frac{p_T - p_C}{\sqrt{p(1 - p)\left(\frac{1}{n_T} + \frac{1}{n_C}\right)}}$$

Where,

 p_T and p_C are the proportions of success for the primary endpoint in the treatment and control groups, respectively, *p* is the pooled estimate of the success rate, and

 n_T and n_C are the sample sizes obtained in the treatment and control groups,

respectively. Two sets of (p, p_T , p_C , n_T , n_C) will be obtained: one at the interim analysis and one at end of the study.

B. Analysis of the Secondary Effectiveness Endpoints

The following describes the analysis techniques to be used for each of the secondary endpoints. To control the family-wise type I error rate at 5%, the Hochberg step-up procedure will be utilized (Hochberg, 1988).

a. FEV₁

Difference between study arms in 'absolute change from baseline' for FEV1 score at 1 year. Descriptive statistics will include means, standard deviations and 95% confidence intervals. An analysis of covariance (ANCOVA) with factor of treatment and baseline FEV1 as a covariate will be used to test the difference between treatment arms. P-value will be adjusted for multiple imputation.

b. 6-Minute Walk Distance (6MWD)

Difference between study arms in 'absolute change from baseline' for 6MWD at 1 year. Descriptive statistics will include means, standard deviations and 95% confidence intervals. An analysis of covariance (ANCOVA) with factor of treatment and baseline 6MWD as a covariate will be used to test the difference between treatment arms. P-value will be adjusted for multiple imputation.

c. St. George's Respiratory Questionnaire (SGRQ)

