20.3.1 Sample Size Rationale

The results of two prospective studies were used to inform the sample size estimation. The Endobronchial Valve for Emphysema Palliation Trial ("VENT Pivotal Trial", IDE#G020230, NCT00129584) was a multi-center, prospective, randomized, controlled study conducted at sites in both the United States and Europe to assess the safety and effectiveness of using the Zephyr EBV device for palliating symptoms associated with severe heterogeneous emphysema. Four hundred ninety two (492) participants were enrolled into the study and randomized to Zephyr EBV Treatment or medical management (control) [16,17]. The Chartis Pulmonary Assessment System study is a recently completed prospective post-market study that was conducted in Germany, The Netherlands, and Sweden. The primary objective of the study was to quantify the accuracy of the Chartis System when used to identify targeted treatment lobes as having or not having inter-lobar CV in patients with emphysema who were to be treated using endobronchial valves (26). The results of both the VENT Study and the Chartis System study showed that treatment effect with the endobronchial valve is correlated with lack of inter-lobar CV [16,17,25].

Patients in the VENT Study and in the Chartis Study who were considered to have little or no inter-lobar CV contributed the information used for the sample size estimate. Patients who have little or no lobar CV in the targeted treatment lobe are expected to be good responders to endobronchial valve treatment. For the sample

size estimate, a 'responder' was considered to be a study participant who had $\geq 15\%$ improved FEV₁ after EBV treatment.

Based on the results of these studies, the responder rate in the EBV Study Treatment Group is expected to be approximately 35% at 1 year. The responder rate for the control group is not expected to exceed 10% at 1 year. Assuming a two-sided 0.05 alpha level, study power of 90%, and 2:1 allocation random assignment, a sample size of 147 will be adequate to test for superiority.

The study sample size will be increased to 183 in order to allow for 20% lost to follow-up and incomplete data. Each study site will be allowed to enroll a maximum of 25 study participants.

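### The SAP gives two final success thresholds for the primary endpoint: two-sided p<0.05 (Z of 1.96) in the Definition of Study Success, and Z of at least 2.004 (nominal p about 0.0451) in Section IV.A

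*SAP*

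**What the plan says.** The current SAP (revised 26 October 2017, replacing Protocol Appendix 19) states the primary decision rule twice.

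- **Analysis Summary, Definition of Study Success.** The study succeeds if the percentage of participants with at least 15% FEV1 improvement "differs significantly (two-sided test at p<0.05) in favor of the treatment group at 1 year". The paragraph mentions no interim analysis, adjusted boundary or overall level, and does not refer to Section IV.A.
- **Section IV.A, interim look.** The analysis takes place "when 74 (50% of the total 147) study participants have completed the 1-year follow-up". A power-family spending function "will be used to preserve an overall type I error rate of 0.05 for the study", and "the value of the Z-statistic must exceed 2.571 (nominal alpha <0.01) for the null hypothesis to be rejected at this interim look". On crossing that bound, the SAP adds: "This observation may provide evidence to stop the trial early".
- **Section IV.A, final look.** If the trial has not stopped, "the final Z-statistic must be greater than or equal to 2.004 in order to reject the null hypothesis at the final analysis". The SAP describes this as the overall two-sided 5% level, and Table 2 gives it a nominal alpha of 0.04511.

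Elsewhere (the SAP's Interim Analysis paragraph; Protocol 7.6 and 20.7) the interim's stated purpose is only to decide whether control participants may continue to cross over.

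**The concern.** A two-sided p below 0.05 is a Z beyond 1.96. A final Z from 1.96 up to 2.004 therefore meets the Definition of Study Success but does not reject the null hypothesis under Section IV.A. The SAP has no rule saying which text governs.

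This is the success criterion for the sole primary endpoint of a trial meant to support premarket approval. With two thresholds on paper, a result in the band could be argued either way once it is known. The summary line also leaves out the adjustment that Section IV.A relies on to hold the overall 5%.

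**Working it through.** **Inputs.** From SAP Section IV.A: alpha = 0.05, phi = 2.3, t = 0.5, bounds 2.57057 and 2.00360, and the pooled two-proportion Z. From Protocol 20.3.1: responder rates of 35% and 10%, 147 evaluable participants, 2:1 allocation. From the SAP Study Design paragraph: 190 enrolled. Assumed here, because the documents do not give them: a 49/25 split at the interim and 127/63 at the end.

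**1. Reproduce Table 2.** Alpha spent at the interim = 0.05 × 0.5^2.3 = 0.01015, so the interim bound is 2.5706. The final bound c solves 1 − P(|Z1| < 2.5706, |Z2| < c) = 0.05, with (Z1, Z2) bivariate normal and correlation √0.5. This gives c = 2.0036, a nominal two-sided p of 0.0451. Table 2 is correct.

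**2. Error rate under each reading (t = 0.5).**

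| Rule | Two-sided error | Favouring EBV |
|---|---|---|
| Final test only, 1.96 | 5.00% | 2.50% |
| Final test only, 2.004 | 4.51% | 2.26% |
| 2.571 at interim, then 2.004 | 5.00% | 2.50% |
| 2.571 at interim, then 1.96 | 5.47% | 2.73% |

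The excess in the last row needs two conditions together: p<0.05 is applied as the nominal final level, and rejection at the interim counts as success.

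**3. Results with opposite verdicts.** Z = (pT − pC) / √[p(1 − p)(1/127 + 1/63)], where 1/127 + 1/63 = 0.02375.

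- 24/127 v 5/63 (18.9% v 7.9%): pooled p = 29/190 = 0.1526; Z = 0.1096/0.0554 = 1.978; p = 0.048.
- 32/127 v 8/63 (25.2% v 12.7%): pooled p = 40/190 = 0.2105; Z = 0.1250/0.0628 = 1.989; p = 0.047.

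Both are successes under the summary definition and failures to reject under Section IV.A.

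**4. How likely the band is.** The exact binomial probability that Z falls from 1.96 up to 2.004 is 0.24% at 35% v 10%, where Z reaches 2.004 with probability 97.8%. Against a 10% control rate the band's probability is at most about 1.7% (1.73% at 21% v 10%).

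**5. Error with binomial data.** Simulating the SAP's pooled Z with the interim look counted as success (1,000,000 runs per rate), false success favouring EBV is:

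| Null responder rate | Final bound 1.96 | Final bound 2.004 |
|---|---|---|
| 10% | 2.09% | 1.80% |
| 15% | 2.23% | 2.02% |
| 20% | 2.37% | 2.19% |
| 27% | 2.50% | 2.31% |

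**6. Information fraction.** Table 2 rests on 74 of 147, but the SAP reports "A total of 190 study participants were enrolled". Protocol 20.3.1 allowed for 20% loss: "The study sample size will be increased to 183 in order to allow for 20% lost to follow-up and incomplete data". The documents do not give the final evaluable number, so the table shows a range, keeping the 0.01015 allotted to the interim.

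| Missing at 1 year (assumed) | Fraction | Final bound for 5% | Overall error if 2.004 is kept |
|---|---|---|---|
| 20% | 74/152 | 2.005 | 5.02% |
| 10% | 74/171 | 2.011 | 5.07% |
| None | 74/190 | 2.016 | 5.12% |

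**The case against.** The best defence is that p<0.05 in the summary means the study's overall level. Section IV.A itself links 2.004 to the overall two-sided 5%, so on that reading the two texts agree. Section IV.A is also the more specific text and is mandatory in tone, and 1.96 is printed nowhere. The Analysis Summary is abbreviated in other places too: its primary endpoint omits the post-bronchodilator condition. An analyst following Section IV.A has no open choice.

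Much of this stands. It makes 2.004 the likely intended rule and weakens any suggestion of a free choice after the fact. But the success definition does not say overall or adjusted and does not point to Section IV.A. A formal definition should not need inference to give one verdict.

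A second objection is that 5.47% belongs to a hybrid rule stated in neither place, since the success definition is evaluated at 1 year and the interim is described as serving crossover. That is fair, and the figure is conditional for this reason. Yet the SAP also says the null can be rejected at the interim and that crossing may support stopping. If the interim served crossover alone, 1.96 would be valid and 2.004 needlessly strict, so one text would still have to change.

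Third, success counts only in one direction, and the simulated error with 1.96 stays at or below about 2.5% for null rates of 10% to 27%. This is correct and limits the practical harm.

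Lastly, the information-fraction point is a separate matter worth at most about 0.12 percentage points. It is kept only as a conditional note.

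**Conclusion.** The concern holds. As written, the success definition and Section IV.A give opposite verdicts for a final Z from 1.96 up to 2.004, that is, for nominal p between about 0.0451 and 0.05. Section IV.A and Table 2 are arithmetically sound; the summary line is the one to change.

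The numerical effect is small: a 0.24% chance of landing in the band at the design rates, and at most about 0.47 percentage points of two-sided error, the latter only if both conditions in step 2 are met. These figures rest on the assumed 127/63 split and, for the error rates, on t = 0.5. The case for correcting it lies in the role of the sentence as the primary decision rule, not in the size of the inflation.

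**What to change.** Make these changes before the final analysis:

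1. Rewrite the Definition of Study Success so that success at the final analysis requires a primary-endpoint Z in favour of EBV at or beyond the group-sequential boundary, citing Section IV.A: Z of at least 2.004, nominal two-sided p of about 0.0451 or less.
2. Add a sentence saying whether crossing 2.571 at the interim is itself study success or informs only the crossover decision.
3. Optionally, recompute the final boundary at the actual information fraction, keeping the 0.01015 allotted to the interim, and use that value in both places. On the range above it would lie between about 2.005 and 2.016.

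The cost is two sentences and, if item 3 is taken up, one boundary calculation. Data collection and sample size do not change.
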